#### Table 5:Abnormal Vital Threshold Values

All vital signs will be displayed in by-participant listings. Clinical interpretations that highlight clinically significant vital signs are included.

Table 6:

### 11. DEPARTURES FROM PROTOCOL PLANNED ANALYSES

#### **Departures from Protocol Analyses**

Analysis Endpoint and SAP Section	Protocol Original Analysis	Updated Analysis	Rationale
Safety: Clinical Laboratories Section 10.14.2	Change from Baseline summaries for hematology and chemistry labs will be presented	Summary of screening labs, only listing of post-baseline labs if collected.	No post-baseline clinical labs are collected, just screening. Change from baseline will not be possible.
Safety: Abnormal Physical Exam Section 10.14	A summary of abnormal physical exams will be presented.	No physical examination summary or listing	Abnormal physical exams are collected as AEs, so they will be captured there.
Quality of Life (SF-12v2) Section 10.13.5	The SF-12 scores would be scored using the 1998 US norms.	The SF-12 scores will be scored using the 2009 US norms	The 2009 norms should better fit the population than the 1998 norms.

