## 5.2. Study Endpoints

### 5.2.1. Safety Endpoints

Safety assessments will be recorded throughout the study (up to Study Day 270 [ $\pm$ 14 days]) as described in Table 1. All participants will be assessed for:

- Adverse events (AEs) and serious adverse events (SAEs),
- · Abnormal hematology and chemistry laboratory values,
- · Physical examination findings, and
- Vital signs

following signing of the informed consent form (ICF) and throughout the study until the visit on Day 270  $(\pm 14 \text{ days})$  for each treatment group.

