## 10.4. Definitions

#### 10.4.1. Adverse Event

An AE means any untoward medical occurrence associated with the use of a drug in humans, whether or not considered drug related. An AE (also referred to as an adverse experience) can be any unfavorable and unintended sign (e.g., a clinically significant abnormal laboratory finding), symptom, or disease temporally associated with the use of a drug, and does not imply any judgment about causality. An AE can arise with any use of the drug and with any route of administration, formulation, or dose, including an overdose.

Facet Joint Osteoarthritis-related events should not be considered or recorded as AEs or SAEs.

Laboratory abnormalities should not be recorded as AEs or SAEs unless they are associated with clinical signs or symptoms, or require medical intervention. However, each laboratory abnormality (e.g., clinically significant changes detected on hematology, or lab chemistries) independent from any underlying medical condition that requires medical or surgical intervention, or that leads to interruption of study drug infusion or discontinuation, must be

recorded as an AE, or SAE if applicable. If the laboratory abnormality is part of a clinical condition or syndrome, it should be recorded as the syndrome or diagnosis rather than as the individual laboratory abnormality. In addition, laboratory abnormalities or other abnormal test assessments that are associated with signs or symptoms must be recorded as AEs or SAEs if they meet the definition of an AE (or SAE) as described above or in Section 10.4.4.

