## 10.7.2. Localized Signs of Infection or Inflammation at the Injection Site

Events that, in the opinion of the Investigator, may represent localized signs of infection or inflammation at the XT-150 injection site (e.g., pain, erythema, swelling, pruritus, warmth, hematoma, induration) must be recorded as AEs on the CRF. In general, these events will be temporally related to the injection.

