# 14.4. Safety Analysis

All participants who receive any amount of study drug (Safety Population) will be included in the safety analyses.

[figure not shown]
Safety will be evaluated by presenting summaries of AEs, clinical laboratory tests, and vital signs. Safety variables will be tabulated by treatment group.

[figure not shown]
Adverse events will be graded using the CTCAE v5.0 and will be coded using the Medical Dictionary of Regulatory Affairs (MedDRA®), Version 24 or higher. AEs will be collected for each participant from the signing of the informed consent through the last study visit on Day 180.

A treatment-emergent adverse event (TEAE) is defined as an AE that occurs during or after study drug administration. The incidence of TEAEs will be presented by system organ class (SOC) and preferred term (PT), by SOC, PT, and relationship to the study drug administration, and by SOC, PT, and severity. In addition, the incidence of serious TEAEs and TEAEs leading to discontinuation of study drug will be presented by SOC and PT.

Descriptive statistics for clinical laboratory test results, and vital signs, and for changes from Baseline, will be presented by time point. Baseline is defined as the measurement closest to, but prior to, the administration of study drug. Incidences of potentially clinically significant clinical laboratory results, and vital signs, as defined in the SAP, will also be summarized by time point. A summary of abnormal physical examination findings will also be presented.

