#### 4.2. Study Endpoints

#### Safety Endpoints:

- Treatment-emergent adverse events (TEAE).
- Treatment-emergent serious adverse events (SAE).
- Abnormal clinical laboratory tests (chemistry and hematology).
- Vital signs (blood pressure, pulse, respiratory rate, and body temperature).
- Physical examination findings.

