#### **10.14.3.** Clinical Examination of the Back (Injection Site)

Clinical examinations of the back and injection site will be performed regularly during the study. The following examination criteria will be assessed and the proportion of participants with symptoms will be summarized by visit:

- Pain
- Erythema
- Swelling
- Pruritus
- Warmth
- Hematoma
- Induration
- Other skin reactions

Injection site reactions will also be recorded as AEs.

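### SAP 11 drops the physical examination output because abnormal findings are AEs, but Protocol 10.4.1 keeps FJOA-related events out of the AE data, so some findings have no planned output

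*SAP*

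**What the plan says.** The primary objective is the safety and tolerability of a repeat bilateral injection. Protocol 5.2.1 names physical examination findings among the safety endpoints, and SAP 4.2 still lists "Physical examination findings". Protocol 14.4 states: "A summary of abnormal physical examination findings will also be presented".

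The departures table in SAP 11 withdraws that analysis. The updated analysis is "No physical examination summary or listing" and the rationale is "Abnormal physical exams are collected as AEs, so they will be captured there".

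Four other provisions bear on whether the rationale holds:

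- Protocol 10.4.1 defines an AE broadly enough to include an unfavourable, unintended sign, but adds: "Facet Joint Osteoarthritis-related events should not be considered or recorded as AEs or SAEs".
- Protocol 10.7.2 says that possible local signs of infection or inflammation at the injection site "must be recorded as AEs on the CRF".
- SAP 10.14.3 keeps an output for the back and injection-site examination: "The following examination criteria will be assessed and the proportion of participants with symptoms will be summarized by visit". The eight items are pain, erythema, swelling, pruritus, warmth, hematoma, induration and other skin reactions.
- SAP 7.2 says in general terms that listings will include all relevant eCRF data.

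**The concern.** The departure is declared openly. The difficulty is its reason, which assumes that every abnormal examination finding reaches the AE page, while the protocol removes one class of event from that page.

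The removed class matters here because the diseased joint is also the injected joint, and it is injected twice. Normally an event put down to the underlying disease is still recorded and then classed as unrelated; Protocol Table 5 lists disease progression among the explanations for that class. Under 10.4.1, attribution to FJOA keeps the event out of the AE data altogether, so nobody can later compare its frequency between arms. Dropping the separate examination summary and listing removes the place where such a finding could otherwise have appeared as an examination finding. SAP 4.2 meanwhile keeps the endpoint, so a reader of the results could take the absence of reported findings as evidence that there were none.

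**Working it through.** The plan gives no figure to reproduce on this point. The check is a reconciliation of the two documents, followed by a count of examinations.

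**Where an abnormal post-baseline finding goes**

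| Type of finding | AE data | Other planned output |
|---|---|---|
| Possible infection or inflammation sign at the injection site | Yes, Protocol 10.7.2 | SAP 10.14.3, by visit |
| Other new or worsened abnormal sign, not attributed to FJOA | Yes, by the AE definition in Protocol 10.4.1 | None needed |
| Attributed to FJOA, among the eight items (for example pain) | No, Protocol 10.4.1, unless 10.7.2 applies | SAP 10.14.3, by visit |
| Attributed to FJOA, outside the eight items | No, Protocol 10.4.1 | None |

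The SAP 11 rationale is sound for the first two rows. It fails for the third, where SAP 10.14.3 makes up for it. It fails for the fourth, where nothing does.

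**Consistency within the SAP.** SAP 4.2 lists the endpoint, SAP 7.2 promises listings of all relevant eCRF data, and SAP 11 says there will be no listing. If the eCRF holds examination findings, SAP 7.2 and SAP 11 conflict. If it does not, SAP 4.2 names an endpoint with no data source of its own.

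**Number of examinations without an output of their own**

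- Protocol Table 1 schedules the brief physical examination on Days 0, 7, 14, 30, 60, 90, 120, 150, 180, 210, 240 and 270: 12 visits, of which 12 - 1 = 11 are post-baseline.
- With 72 participants all followed to Day 270: 72 x 11 = 792.
- Participants on the single-dose path finish at Day 180 and miss three visits (Days 210, 240, 270), leaving 11 - 3 = 8. If all 72 did so: 72 x 8 = 576.
- If k participants finish at Day 180 and nobody else leaves early, the count is 792 - 3k. Earlier withdrawal lowers it further.

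This counts examinations, not findings. The documents give no rate of abnormal findings and no rate of attribution to FJOA, so the fourth row of the table cannot be sized.

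**The case against.** The strongest reply is that little is lost. The AE definition in Protocol 10.4.1 already takes in new abnormal signs, and 10.7.2 adds to that definition without limiting it. SAP 10.14.3 keeps a by-visit summary that includes pain, and Protocol 9.4, 9.6 and 9.7 place the injection-site check inside the brief examination, so part of each examination is still reported. Worsening in the treated region could also show in VAS change, the participant global assessment and the back-pain medication summaries. The exclusion in 10.4.1 speaks of events, not findings. Neither document describes what the brief examination contains beyond the injection site and, at Day 270, height and weight.

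Most of this stands, and it sets the limits of the point. A reader might infer that every examination output has been removed, or that no remaining output could show local harm. SAP 10.14.3, the AE rules and the patient-reported and medication summaries rule out both readings. A reader might also suppose that blinded examiners will usually blame the disease; the documents give no basis for any frequency.

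Two things remain. VAS and the global assessment are patient-reported efficacy measures and do not stand in for an examiner's finding. Protocol Table 1 and SAP Appendix 1 also schedule the brief physical examination in a row separate from the back examination, and SAP 10.14.3 reports only the latter. As for events against findings, the point assumes that a site which attributes an abnormal finding to FJOA will apply the exclusion to it. That is a reasonable reading, but it is an inference.

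**Conclusion.** The point holds within limits. The reason that SAP 11 gives conflicts with Protocol 10.4.1. As a result, FJOA-attributed examination findings outside the eight items of SAP 10.14.3 have no planned output, although they belong to a safety endpoint that serves the primary objective and that SAP 4.2 still names.

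The number of such findings is unknown. The 792 examinations (576 if all participants ended at Day 180) are an upper bound on examinations that lack an output of their own. It would be tempting to read 792 as a measure of lost safety data, but the documents do not support that: the injection-site part is still reported, and other new abnormal signs meet the AE definition.

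The conclusion rests on two assumptions: that sites apply the 10.4.1 exclusion to findings as well as to events, and that the brief examination can yield findings outside the eight items. It should be corrected because it bears on what the safety results can support, and correction is cheap.

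**What to change.** The change depends on what the eCRF holds.

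- **If it holds examination findings:** replace the physical examination row in SAP 11. Add to SAP 10.14 a by-arm summary of participants with abnormal post-baseline findings, whatever the attribution, and a by-participant listing. This meets Protocol 14.4 and removes the conflict with SAP 4.2 and SAP 7.2. The cost is one table and one listing.
- **If it does not hold them:** correct the rationale in SAP 11 and reconcile it with SAP 4.2 and Protocol 10.4.1. State in the SAP and the CSR that FJOA-attributed examination findings outside SAP 10.14.3 were not captured, so no between-arm safety conclusion can be drawn on them. The cost is a few lines of text and a stated limitation.

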#### Protocol: XT-150-1-0302 Statistical Analysis Plan, Version 3.0

### APPENDICES

#### **Appendix 1 Schedule of Events**

Scheduled Event	Screen	Baseline a and Dosing		Follo	Follow-up Dosing				Follow-Up					
Study Day	-30 to -1	0	7 (±1)	14 (±1)	30 (±2)	60 (±7)	90 (±7)	120 (±7)	150 (±7)	180 b (±7)	210 (±7)	240 (±7)	270 (±14)	
Informed Consent c	X													
Complete Medical History, Demographics and Physical Examination d	X													
Record Prior Medications e	X	Х												
Confirmation of FJOA by Imaging f	X													
Lidocaine Facet Selection	х													
Efficacy Assessments														
VAS	X g	X g	x	x	X	X	X	Х	X	X	X	X	x	
Oswestry Disability Index		Х	x	x	X	X	X	Х	X	X	X	X	X	
International Physical Activity Questionnaire (IPAQ)		х	x	x	x	x	X	Х	x	x	x	x	x	
SF12		Х	X	X	X	X	X	Х	X	X	X	X	X	
Participant Global Assessmenth		Х	x	X	X	X	X	Х	X	X	X	X	x	
			X	X	X	X	X	Х	x	x	x	x	X	
Clinical Assessments	1		1	1	1	1			I	1	1	1	 	
Record Height and Weight, Calculate BMI	Х												Х	

October 13, 2023

#### XALUD THERAPEUTICS, INC. Study Drug: XT-150

#### Protocol: XT-150-1-0302 Statistical Analysis Plan, Version 3.0

Scheduled Event	Screen	Baseline a and Dosing	Follow-up				Dosing	Follow-Up					EOS
Study Day	-30 to -1	0	7 (±1)	14 (±1)	30 (±2)	60 (±7)	90 (±7)	120 (±7)	150 (±7)	180 b (±7)	210 (±7)	240 (±7)	270 (±14)
Vital Signs	X	Х	Х	Х	Х	X	X	Х	X	X	X	Х	X
Clinical Exam of the Back (injection site)	X	Х	Х	X	Х	X	X	Х	X	X	X	X	Х
Brief Physical Examination		Х	Х	X	X	X	X	Х	X	X	X	X	X
Record AEs		Х	Х	X	X	X	X	Х	X	X	X	X	X
Record SAEs		Х	Х	X	X	X	X	Х	X	X	X	X	Х
Record Concomitant Medications		Х	Х	Х	Х	X	X	Х	X	X	X	X	Х
Laboratory Assessments													
HIV, Hepatitis B and C	X												
Serum Chemistries	X												
CBC with Differential and Platelet Count	X												
Pregnancy Test (for WOCBP) j	X						X						Х
Whole Blood for Plasmid DNA Biodisposition k		Х	Х	Х	Х								
Serum for IL-10 and Anti-IL-10 Antibody Assessments		Х	Х	Х	X	X	Х			X			Х
Study Drug Administration													
Enroll Participant 		Х											
Administer Study Drug m		Х					X 						

a Baseline assessments are performed before injection on Day 0 OR up to one day before study drug administration. Vital signs also assessed at 1 hour after study drug administration.

b Participants who were enrolled in the study prior to implementation of Protocol Version 3.0 08Jun2022 and either are past their Day 90 visit or do not consent to the Day 90 dose will complete the study at Day180. At this visit, all EOS procedures should be completed.

c Informed consent must be obtained before initiating any study procedures.

d Obtain demographics (age, race, gender) and complete, relevant, medical, and surgical history (including currently active conditions and inactive pain conditions diagnosed) at the Screening visit. Update medical and surgical and pain treatment history at the baseline visit. The physical examination includes the injection site for infections or reactions.

e Record prior medications, including prescription and nonprescription medications and herbal supplements. Update prior medications at the baseline visit.

f For inclusion in the study, the participant must have sufficiently severe facet arthropathy of lumbar facets as determined by imaging (e.g., MRI, CT) to establish an underlying basis of disease, as determined by usual bony and ligamentous signs of OA. Use of historical images is permitted if the images were obtained within the last 12 months.

g Participants must have a VAS score of at least 50 out of 100 at Screening and at Baseline in order to qualify for study inclusion and treatment.

h Participant global assessment will be recorded by answering the question: "Considering all the ways that facet pain, the pain that brought you into this study, affects you, how are you doing today?" on a scale of 1 to 5, 1 being very good (asymptomatic and no limitation of normal activities) to 5, very poor (very severe, intolerable symptoms and inability to carry out normal activities)

i Pain therapy and concomitant medications are recorded

j A serum pregnancy test will be performed for WOCBP at Screening and Day 270/EOS. A urine pregnancy test will be performed for WOCBP at Day 90 prior to study drug administration.

k Whole blood for PCR analysis of DNA plasmid biodisposition will be drawn at Baseline, before study drug injection then approximately 4 hours after injection, then on Days 7, 14, and 30 scheduled clinic visits.

 Verify that the participant meets all study inclusion and exclusion criteria before enrollment as close to study drug dosing as possible.

m Participant will receive one intra-articular, 1-mL dose of study drug by intra-articular injection to the facet capsule at time zero. Participant to be monitored for 4 hours after administration for signs of study drug reaction.

Key: AE = adverse event; BMI = body mass index; CBC = complete blood count; FJOA = facet joint osteoarthritis; IL-10 = interleukin 10; SAE = serious adverse event; SF12 = short form health survey; VAS = visual analog scale of pain intensity; WOCBP = women of childbearing potential
